**Randomized controlled trial of social cognition interaction training
and a therapeutic alliance focused therapy among persons with
Schizophrenia.**

Clinicaltrial.gov ID NCT02380885

Scientific background

Schizophrenia is associated with impairments in both interpersonal and intrapersonal functioning, which in turn, hinders quality of life (QoL). These impairments are so extensive that various clinicians and researchers view them as a major feature of schizophrenia characterized by difficulties in understanding the social environment and the individual's place within it (Penn, Corrigan, Bentall, Racenstein, & Newman, 1997; Stanghellini, 2000). These impairments are relatively non-responsive to antipsychotic medications (Bellack, Schooler, & Marder, 2004) and are reported by patients as their greatest unmet need (Coursey, Keller, & Farrell, 1995; Middelboe et al., 2001). One strong mediator of social functioning impairments in schizophrenia is disturbance in social cognition (i.e., the cognitive processes that underlie social interaction; Couture, Penn, & Roberts, 2006; Brüne, Abdel-Hamid, Lehmkämper, & Sonntag, 2007). The growing recognition of the devastating impact of social cognition deficits in schizophrenia, have generated attempts to develop interventions that target social cognition as a means to improve social functioning and QoL. One such intervention is Social Cognition and Interaction Training (SCIT; Roberts, Penn, & Combs, 2006). SCIT is a manualized, group-based intervention that has demonstrated efficacy in improving social cognition and social functioning in both inpatient and outpatient samples (Combs et al., 2007a; Combs et al., 2009b; Roberts & Penn, 2009; Roberts, Penn, Labate, Margolis, & Sterne, 2010). SCIT was developed to address the three core domains of social cognition that are disrupted in schizophrenia: emotion perception, theory of mind, and attributional style. The major theoretical assumption underlying SCIT is that schizophrenia is associated with a number of social cognitive distortions and impairments. These include jumping to conclusions (Garety, Hemsley, & Wessely, 1991), attribution bias (Bentall, 1994), as well as problems with Theory of Mind (ToM; Frith, 1992) and emotion perception. Because these cognitive impairments are linked to the mental operations underlying social interactions, such as the human ability and capacity to perceive the intentions and dispositions of others (Brothers, 1990), they interfere with social QoL and functioning.

The proposed study assessed both the theoretical assumptions and the effectiveness of the SCIT intervention with persons diagnosed with schizophrenia. The SCIT intervention emphasizes a set of techniques designed to ameliorate the social cognitive deficiencies and biases to promote change. Accordingly, this study will assess both potential mediating processes, such as emotion perception and ToM, that are thought to be limited and distorted by schizophrenia, as well as social functioning and QoL. To test whether any positive change can be attributed specifically to SCIT, we compared its impact to a different intervention, called Therapeutic Alliance Focused Therapy (TAFT). TAFT is based on the system of observing family therapy alliance (Friedlander, Escudero, & Heatherington, 2006) and focuses on the therapeutic alliance. Both interventions (experimental groups) were compared to control group of treatment as usual (TAU).

Method

Research Setting

The current randomized controlled trial (RCT) was an intervention study that assessed the effectiveness of SCIT versus TAFT in a psychiatric community setting in Israel (Clinicaltrial.gov ID NCT02380885). Data were collected between the years 2014 and 2018. Previous studies

derived from this larger project were conducted on the basis of baseline partial samples of the current study (25, 26). Approval for the study was obtained from the ethics committee of the Department of Psychology at Bar-Ilan University, as well as from two psychiatric hospital committees. After receiving a detailed explanation of the study, all research participants provided written informed consent. Data were collected by an experienced mental health practitioner who was trained to administer.

Statistical Analysis:

Analyses were computed using Predictive Analytics SoftWare (PASW, Version 25.0). To test whether the groups differed in their baseline scores on the scales and whether there were differences between participants who did and did not complete Time 2 assessments, two-way ANOVAs were performed. To examine improvement in the outcomes (SQoL, FEIT, Faux Pas task, SSPA, and AIHQ), mixed repeated measures ANOVAs were used with time (pre, post) and group (SCIT, TAFT, and TAU) as factors. A mixed repeated-measures ANOVA allows for an examination of the extent to which participants improved over time regardless of group, as well as whether they improved significantly more over time in one group versus the other (group-time interaction). To assess the overall effect sizes, partial eta squared (η^2) was computed with $\eta^2 = .01$ indicating small, $\eta^2 = .059$ medium, and $\eta^2 = .138$ large effects (37). In case of a significant effect, a paired two-sample t test was conducted for each group comparing preand post-results. Effect sizes of paired tests were reported with Cohen's d (37) with $d = .2$, indicating small; $d = .5$, medium; and $d = .8$ large effects. To examine whether the therapeutic alliance was associated with the change in the research variables, we performed a multiple regression, with the difference in each variable (difference between time 1 and time 2) as the dependent variable, and group (0-SCIT, 1-TAFT) and the four dimensions of the therapeutic as the independent variables.

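### No analysis has a therapy-group term: if SCIT was given in groups and change is correlated within them, the SCIT paired test, and with similar arm variances the group-by-time test, uses too small an error term

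*Combined protocol and SAP*

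**What the plan says.** The Scientific background section of the combined protocol and SAP introduces the intervention with the words "SCIT is a manualized, group-based intervention that has demonstrated efficacy". This describes SCIT in general. No later section says how SCIT or TAFT was delivered in this trial, or gives the number or size of therapy groups.

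The same section states the purpose of the active comparator: "To test whether any positive change can be attributed specifically to SCIT, we compared its impact to a different intervention", namely TAFT. A TAU arm is the third comparison.

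The Statistical Analysis section lists the models:

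- Outcomes: "mixed repeated measures ANOVAs were used with time (pre, post) and group (SCIT, TAFT, and TAU) as factors". The interaction is the test of "whether they improved significantly more over time in one group versus the other (group-time interaction").
- Follow-up: "In case of a significant effect, a paired two-sample t test was conducted for each group comparing preand post-results".
- Alliance: a multiple regression of change on "group (0-SCIT, 1-TAFT) and the four dimensions of the therapeutic as the independent variables".

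Group means trial arm throughout. There is no random effect for therapy group, no cluster-robust error and no other allowance for clustering.

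**The concern.** People treated together share sessions, therapists and peers. Their changes may therefore be correlated, and because this arises after allocation, randomisation does not remove it. The SCIT mean change then varies more from one realisation of the trial to another than the spread of individual changes suggests. A test that counts every SCIT participant as an independent observation uses too small an error term.

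The interaction is the plan's test of whether change is specific to SCIT, and it is applied to five named outcomes. If shared group influences enter it as if they were independent observations, it rejects a true null more often than its nominal level. A cautious reading of a SCIT-specific result would then be needed.

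**Working it through.** **Inputs.** The documents give no sample size, alpha, ICC, group size or number of groups, so there is no figure of the plan to reproduce. Assumed: SCIT in k groups of m, with (m, k) = (6, 5) or (8, 4), so 30 or 32 per arm; equal arms; equal total variance s²; TAFT and TAU independent; no true change in any arm; two-sided 5%.

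**Step 1: variance of the SCIT mean change.** With ICC ρ of change,

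Var(mean) = (s²/n) × [1 + (m−1)ρ].

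The bracket is the design effect. At ρ = 0.05 and m = 6 it is 1 + 5 × 0.05 = 1.25. At ρ = 0.10 and m = 8 it is 1 + 7 × 0.10 = 1.70. The SCIT paired test uses about s²/n instead, and because its error term comes from the SCIT arm alone, no condition on the other arms is needed.

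**Step 2: the interaction.** With two time points, the group-by-time F test is a one-way ANOVA on change scores. With equal arm variances,

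E[MS between arms] = s² × {1 + (1 − n_SCIT/N)(m−1)ρ/2}, while E[MS error] is at most s².

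With three equal arms, 1 − n_SCIT/N = 2/3, so the factor is 1 + (m−1)ρ/3. This is 1 + 0.25/3 = 1.08 for m = 6, ρ = 0.05, and 1 + 0.70/3 = 1.23 for m = 8, ρ = 0.10. The numerator is inflated and the denominator is not.

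**Step 3: type I error by simulation** (100,000 runs per row, change scores with unit total variance):

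| m, k | ICC | Design effect | Interaction | SCIT paired, ungated | SCIT paired after significant interaction, either direction |
|---|---|---|---|---|---|
| 6, 5 | 0 | 1.00 | 4.9% | 5.0% | 1.5% |
| 6, 5 | 0.02 | 1.10 | 5.4% | 6.1% | 1.9% |
| 6, 5 | 0.05 | 1.25 | 6.3% | 7.8% | 2.7% |
| 6, 5 | 0.10 | 1.50 | 7.7% | 10.7% | 4.0% |
| 8, 4 | 0 | 1.00 | 5.0% | 4.9% | 1.6% |
| 8, 4 | 0.02 | 1.14 | 5.8% | 6.5% | 2.1% |
| 8, 4 | 0.05 | 1.35 | 7.0% | 9.2% | 3.3% |
| 8, 4 | 0.10 | 1.70 | 8.9% | 13.1% | 5.1% |

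**Step 4: false SCIT benefit.** The last column counts both directions, and by symmetry about half of it is improvement: 2.7/2 = 1.35% up to 5.1/2 = 2.55% at ICC 0.05-0.10. Counted directly, and including a layout of 6 groups of 5 (1.2% at ICC 0.05), the range is about 1.2-2.6%, against 0.7-0.8% at ICC 0. If the gate on the paired tests also opens on a significant time effect, the two-sided figure is 4.3-8.0% (2.6% at ICC 0), so about 2.2-4.0% in the direction of benefit (1.3% at ICC 0).

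**Step 5: the variance condition** (ICC 0.05-0.10). With equal arm sizes and SCIT variance 0.5-1.5 times that of the other arms, interaction error is 5.7-10.1%. With TAFT and TAU at 45 each and SCIT variance halved, it is 4.9-6.5%, so the excess can vanish.

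**Step 6: the regression.** With four alliance scores correlated 0.4 and alliance ICC 0.1-0.2, error at ICC 0.05-0.10 is 6.3-9.2% for the arm coefficient and 5.0-5.7% for the alliance coefficients.

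**The case against.** **The premise is not shown for this trial.** The group-based description is general background, and nothing reports how SCIT was run here. This stands. A reader might infer that the analysis is certainly wrong. The documents support only a conditional statement: group delivery is the natural reading, but it is not stated.

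**No size comes from the documents.** This also stands. Non-completion of Time 2, which the plan anticipates by comparing completers with non-completers, would shrink the analysed groups and lower the design effect. With 6 groups of 5, interaction error is 6.0-7.3% at ICC 0.05-0.10.

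**The interaction figure is not the risk of a false SCIT claim.** A reader might take 6-9% as the chance of wrongly declaring SCIT beneficial. It is not. The test is a non-directional three-arm omnibus, which also rejects when SCIT looks worse or when TAFT and TAU differ. The plan runs paired tests only after a significant effect, so the ungated 8-13% is not the error of the planned sequence. With the interaction as gate, false SCIT benefit stays at about 1.2-2.6%. This does not remove the point, because the rate is still some two to three times its value at ICC 0, and the gate does not correct the interaction itself.

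**The regression is peripheral.** Agreed. Its stated aim is the association of alliance with change, and those coefficients are nearly unaffected.

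**A model resting on 3-4 degrees of freedom should not overrule the planned test.** Agreed. With so few groups, failure to confirm may reflect low power.

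**Conclusion.** The concern holds conditionally and is moderate in size. It is established that no planned analysis allows for therapy-group clustering, although the intervention is described as group-based. If SCIT was delivered in groups and the ICC of change is above 0, the SCIT paired test understates its error. The group-by-time interaction does so too when arm variances are similar. Under the assumed layouts and ICC 0.05-0.10, this means about 6-9% for the interaction and 8-13% for the paired test on its own.

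The documents do not support saying that any result is false, that the trial's SCIT conclusion fails, or that TAFT has the same problem, since its format is not given. Baseline comparisons and the TAU paired tests are not affected. The ICC, group sizes, arm sizes and alpha are all assumptions here; only the trial's own data can replace them.

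**What to change.** **First,** state how SCIT and TAFT were delivered, with the number and size of therapy groups and whether membership was stable. This costs little and settles the condition.

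**Second, if SCIT was group-delivered,** report a partially nested mixed model beside the planned ANOVA:

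- outcome: change, or post score adjusted for baseline;
- a random therapy-group effect in SCIT, also in TAFT if it was grouped, and none in TAU;
- arm-specific residual variances;
- Satterthwaite or Kenward-Roger degrees of freedom.

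If the pre and post rows are kept, the random effect must be therapy group by time, because a random intercept alone cancels from the change contrast. Give the interaction and within-SCIT intervals from this model, and the estimated ICC. Where the two analyses differ, qualify the SCIT-specific conclusion, without treating the new model as a veto. For the alliance regression a therapy-group term is a secondary addition.

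**Cost.** The documents report that "Data were collected between the years 2014 and 2018", so this is a re-analysis without new data. It needs a therapy-group identifier, which the documents do not mention and which is assumed retrievable.

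The costs in precision were gauged with a simplified stand-in, a three-arm Welch test with the SCIT variance taken from therapy-group means. Its type I error was 5.3-5.8% at ICC 0.05-0.10. For a 0.8 SD change in SCIT only, interaction power falls from 87-89% to 66-76% at those ICCs, and from 89-91% to 83% at ICC 0. Part of the higher figures at ICC 0.05-0.10 reflects the inflated error rate. For 0.5 SD, power falls from 49-52% to 34-39% at ICC 0.05-0.10. The within-SCIT error margin is 1.4-1.9 times as wide at those ICCs. The ICC will be imprecise: the cluster variance is estimated at zero in 34-44% of data sets, in which case a comparison using therapy-group means is a reasonable supplement.

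### The named outcome methods need both scores, so by inference participants without Time 2 drop out of them; no missing-data method is stated, and change is tested without baseline adjustment

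*Combined protocol and SAP*

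**What the plan says.** All of the analysis text is in the Statistical Analysis section of the combined protocol and SAP.

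- **Attrition.** Besides comparing the groups at baseline, the plan says that, to test "whether there were differences between participants who did and did not complete Time 2 assessments, two-way ANOVAs were performed". It gives neither the number of non-completers nor their reasons.
- **Main analysis.** For the five outcomes (SQoL, FEIT, Faux Pas, SSPA, AIHQ), "mixed repeated measures ANOVAs were used with time (pre, post) and group (SCIT, TAFT, and TAU) as factors". The treatment question rests on the group-time interaction. No covariate is named.
- **Follow-up.** After a significant effect, "a paired two-sample t test was conducted for each group".
- **Alliance regression.** This is fitted "with the difference in each variable (difference between time 1 and time 2) as the dependent variable", on group (SCIT or TAFT) and four alliance dimensions. The baseline score is not a predictor.

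The document contains no analysis set, intention-to-treat statement, imputation, likelihood-based model or missing-data sensitivity analysis.

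The Scientific background section shows what the contrasts must support: "To test whether any positive change can be attributed specifically to SCIT, we compared its impact to a different intervention", namely TAFT. It adds that both active arms were compared with TAU.

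**The concern.** A person with a Time 1 score only has no pre-post difference, so none of the named outcome methods can use that person. The comparison of SCIT, TAFT and TAU then becomes a comparison of completers, and randomisation protects it only if loss to Time 2 does not distort the arms differently. The three arms offer different experiences, so equal rates of and reasons for leaving cannot be taken for granted. The plan gives no means of judging how far the missing scores could move SCIT versus TAFT, the contrast used to claim specificity.

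A separate cost arises even with complete follow-up. Baseline scores were collected but are used only by subtraction, which is less efficient than adjusting for them.

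**Working it through.** The documents give no sample size, dropout rate, SD or pre-post correlation (rho), so there is no figure to reproduce. The inputs below are assumptions. Scores have SD 1 at both times, higher is better, and there is no true effect.

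**1. What the interaction tests.** With two time points the within-person contrast is D = Time 2 - Time 1, and the group-time interaction tests whether mean D is equal across groups. In simulated three-arm data the split-plot interaction F and the one-way ANOVA F on D were both 2.766. The main test is therefore an unadjusted change-score test that needs both scores.

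**2. Precision without dropout.** Contrast variance is proportional to 2(1 - rho) for change and to 1 - rho^2 with baseline adjustment. The ratio is 2(1 - rho)/[(1 - rho)(1 + rho)] = 2/(1 + rho), so the excess is 2/(1 + rho) - 1:

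| rho | 0.3 | 0.5 | 0.6 | 0.7 | 0.8 |
|---|---|---|---|---|---|
| Excess variance of change score | 54% | 33% | 25% | 18% | 11% |

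Selective dropout alters these figures somewhat. In an arm with 25% dropout and log-odds 1.0 per SD, the excess at rho 0.5 is 29% if dropout depends on baseline and 38% if it depends on the part of Time 2 that baseline does not predict. At rho 0.6 it is 22% and 29%.

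**3. Bias from baseline-related dropout in one arm.** Let low scorers leave that arm more often (logistic, log-odds 1.0 per SD), with random loss at the same rate elsewhere. Numerical integration gives a completers' mean baseline shift c of 0.133, 0.213 and 0.292 SD at 15%, 25% and 35% dropout. Mean change shifts by -(1 - rho)c. At 25% dropout:

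- rho 0.5: -(0.5)(0.213) = -0.107 SD
- rho 0.6: -(0.4)(0.213) = -0.085 SD
- over the wider range, rho 0.3: -(0.7)(0.213) = -0.149 SD; rho 0.8: -(0.2)(0.213) = -0.043 SD

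A simulation with 1,000,000 per arm gave -0.106 and about -0.087 SD at rho 0.5 and 0.6, and 0.00 after adjusting for baseline. The same selection in all arms at equal dropout gave 0.00. With that selection in both arms but 35% versus 15% dropout, the bias is -(0.5)(0.292 - 0.133) = -0.080 SD at rho 0.5 and -(0.4)(0.159) = -0.064 SD at rho 0.6.

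**4. Bias that adjustment does not remove.** If dropout in one arm depends instead on the unpredicted part of Time 2, the shift is sqrt(1 - rho^2) x c. At 25% dropout this is 0.866 x 0.213, about +0.185 SD, at rho 0.5, and 0.8 x 0.213, about +0.171 SD, at rho 0.6. Adjusting for baseline left it unchanged in simulation.

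**5. On the plan's own scale.** The plan's wording is "To assess the overall effect sizes, partial eta squared", with .01 as small. With one of three equal arms displaced, f2 = (2/9) x bias^2 / [2(1 - rho)], and partial eta squared = f2/(1 + f2). For the baseline-related bias at 25% dropout and rho 0.5, f2 = (2/9)(0.107^2)/1.0 = .0025. Over 15% to 35% dropout and rho 0.5 to 0.6 this bias equals .0008 to .0047, below small throughout. The outcome-related bias equals about .003, .008 and .014 to .015 at 15%, 25% and 35%, above small only at 35%.

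**The case against.** - **Mixed might mean a likelihood-based mixed model**, which would keep people with baseline only. The text does not say so. Time and group as factors, partial eta squared and paired follow-up tests all point to the classical between-within ANOVA. The exclusion nevertheless remains an inference.
- **Attrition was checked.** The two-way ANOVA may have included a group-by-completion term, although the text does not state this. Such a term would bear on whether the baseline gap between completers and non-completers differs by arm, which is close to the condition for bias in step 3. This deserves credit, but it is a diagnostic and corrects nothing. For the outcomes it sees only baseline scores, so it cannot reveal dropout related to the rest of Time 2.
- **Change scores are valid in a randomised trial.** This stands for complete data. A reader might infer that the interaction test is wrong in itself; without dropout it is unbiased, and the point is one of efficiency.
- **The model repairs the smaller bias.** In these scenarios the outcome-related bias is the larger one and survives adjustment. That also stands, and it is why a sensitivity check belongs beside the model.
- **Every size is assumed.** Correct. If very few people missed Time 2, the bias argument largely disappears and only the precision argument remains.

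**Conclusion.** The point holds in limited form. The plan recognises non-completers, states no way of handling them, and names only methods that cannot use them. Its main test is an unadjusted completer change-score comparison.

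The precision loss does not need dropout: 54% to 11% excess variance for rho 0.3 to 0.8. The bias is conditional. It is about -0.11 to -0.09 SD for baseline-related dropout confined to one arm (25% dropout, log-odds 1.0 per SD, rho 0.5 to 0.6), and zero when selection and dropout are the same in all arms.

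A reader might infer that non-completers were excluded by rule, or that the trial's results are biased in a known direction. The documents support neither: no exclusion rule is written, and the amount, causes and balance of Time 2 loss are not given.

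**What to change.** Make the primary comparison of SCIT, TAFT and TAU a likelihood-based model of Time 1 and Time 2 for all randomised participants in their assigned arm, with a common baseline mean and group-by-Time-2 terms. Multiple imputation followed by ANCOVA of Time 2 on baseline is an acceptable alternative. Take the pairwise contrasts from this model, and keep the completer ANOVA and paired t tests as secondary. This gains precision and removes bias from dropout that depends on the modelled baseline scores, not from other causes.

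Report Time 2 loss by arm. Add a short tipping-point check for the main contrasts that shifts missing Time 2 values separately by arm. A contrast moves by the shift times that arm's dropout: at 25% dropout, shifting SCIT alone by -0.75 SD moves SCIT versus TAFT by -0.75 x 0.25 = -0.19 SD, whereas an equal shift in both arms at equal dropout moves it by 0. A joint shift would therefore hide the problem.

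The alliance regression is a separate analysis with a non-randomised predictor and is outside this fix.

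The cost is modest reprogramming on existing data, with no new collection. The estimate may be less favourable, and the authors must defend the range of shifts. Because "Data were collected between the years 2014 and 2018", the reanalysis must be labelled post hoc.

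### Five equally ranked outcomes are tested with no stated primary outcome, significance level or multiplicity rule, and a significant effect is followed up only within arms, not between them

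*Combined protocol and SAP*

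**What the plan says.** The Statistical Analysis section lists five outcomes side by side, "To examine improvement in the outcomes (SQoL, FEIT, Faux Pas task, SSPA, and AIHQ", and says that "mixed repeated measures ANOVAs were used with time (pre, post) and group (SCIT, TAFT, and TAU) as factors". Two effects are read from each model: improvement over time whatever the arm, and the group-by-time interaction. The next step is: "In case of a significant effect, a paired two-sample t test was conducted for each group comparing preand post-results". The section does not say whether the effect that triggers these tests must be the interaction.

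The document gives no primary outcome, significance level, testing order or multiplicity rule, and does not say how many outcomes must be significant to support a conclusion.

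The last paragraph of the Scientific background sets the question. It says "this study will assess both potential mediating processes, such as emotion perception and ToM", and sets these apart from social functioning and quality of life. It gives the reason for the second active arm as "To test whether any positive change can be attributed specifically to SCIT". It describes TAFT as a therapy that "focuses on the therapeutic alliance. Both interventions (experimental groups) were compared to control group of treatment as usual (TAU").

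A separate regression asks whether alliance is associated with change. Its predictors are "group (0-SCIT, 1-TAFT) and the four dimensions of the therapeutic as the independent variables".

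**The concern.** There are two gaps, and both affect what may be concluded.

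The first is multiplicity. With five tests of equal standing and no rule for combining them, any one significant interaction could be presented as the treatment effect, and nothing in this document fixes in advance which outcome carries the conclusion.

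The second is the follow-up. The stated question is comparative: SCIT against TAFT, and each against TAU. A significant three-arm interaction says that the arms differ somewhere, but not where. Paired tests within arms do not locate the difference, because a significant change in one arm and a non-significant change in another is not evidence that the two differ. A reader who follows the plan and sees significant improvement in SCIT but not in TAFT could call the benefit specific to SCIT with no test of that difference behind the claim. If a time main effect also triggers the paired tests, the same pattern could be reported when the interaction is not significant at all.

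**Working it through.** The plan gives no sample size, significance level or error rate, so it has no figure to reproduce.

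**Inputs from the document.** Five outcomes, three arms, two time points. With two time points the group-by-time test is a one-way F test on change scores, with 3 - 1 = 2 numerator degrees of freedom.

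**Assumptions.** 0.05 per test, any one significant interaction read as an effect, equal correlation r between outcomes, normal change scores and 30 per arm, except where stated.

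**Step 1: independent outcomes.** Five: 1 - 0.95^5 = 0.226. Two: 1 - 0.95^2 = 0.0975.

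**Step 2: correlated outcomes** (simulation, 20,000 runs, all nulls true).

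| r | 0 | 0.3 | 0.5 | 0.7 | 0.9 |
|---|---|---|---|---|---|
| At least one false interaction of five | 22.7% | 20.7% | 18.8% | 15.0% | 10.6% |

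The limit at r = 1 is 5%. A separate large-sample run (1,000,000 replicates) gave 21.1% at r = 0.3 and 18.6% at r = 0.5. F tests at 15, 25 and 40 per arm gave 21.0-21.1% and 18.4-18.8%, so the result hardly depends on sample size. For two outcomes the rate is 9.8%, 9.3% and 9.3% at r = 0, 0.3 and 0.5.

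**Step 3: if the five time effects also count.** Ten tests give 1 - 0.95^10 = 0.401 if independent, about 38% at r = 0.3 and 34% at r = 0.5.

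**Step 4: the within-arm follow-up.** One outcome, 30 per arm, SCIT and TAFT truly equal, both better than TAU by the shift shown (in SDs of change). The table gives the share of trials in which the interaction is significant and exactly one of the SCIT and TAFT paired tests is significant.

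| Mean change in TAU | Shift 0.3 | Shift 0.4 | Shift 0.5 |
|---|---|---|---|
| 0 | 13% | 16% | 15% |
| +0.2 SD (improves) | 6% | 5% | 3% |
| -0.2 SD (worsens) | 8% | 18% | 29% |

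The paired tests depend on absolute change, so the rate moves with TAU's own course. It also moves with sample size: with no TAU change and 80 per arm it is 1-15%. A direct SCIT-TAFT contrast after a significant interaction, both at 0.05, is falsely significant in 3.6%, 4.5% and 4.4% at the three shifts. Adding the same change to every arm leaves the interaction and the contrast untouched, so these figures do not depend on what TAU does.

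**Step 5: does the remedy hold the error rate?** Five interactions at 0.01: 1 - 0.99^5 = 0.049 if independent; simulated 4.7% at r = 0.3 and 4.3% at r = 0.5. Next, let SCIT equal TAFT and both beat TAU by 0.8 SD on every outcome, and count any false SCIT-TAFT contrast after a passing interaction, at r = 0 / 0.3 / 0.5:

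- five outcomes, both steps at 0.05: 22.5% / 21.0% / 18.8%
- five outcomes, both steps at 0.01: 4.7% / 4.6% / 4.2%
- two outcomes, both steps at 0.025: 4.7% / 4.9% / 4.8%

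**Step 6: power.** Noncentral F with 2 and 3 × (30 - 1) = 87 degrees of freedom. Noncentrality that gives 80% at 0.05 gives 70.9% at 0.025 and 58.2% at 0.01; 90% becomes 83.9% and 74.0%. With f² = η²/(1 - η²) and noncentrality f² × 3n, the number per arm for 80% power is:

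| Plan's benchmark | 0.05 | 0.025 | 0.01 |
|---|---|---|---|
| Medium (.059) | 53 | 63 | 76 |
| Large (.138) | 22 | 26 | 31 |

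**The case against.** The strongest reply is that the error figures rest on inputs the document does not supply. That is true of the 0.05 level, the any-one-counts rule, the correlations and the sample size. On a reading in which functioning and quality of life carry the conclusion and the other measures are mediators, the inflation is about 9-10%, not 19-21%. The background does draw that distinction, but the analysis section does not use it to rank the tests, so the reading is available without being binding.

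A second reply is that a primary outcome may be named in the trial's registration. The document cites the registration number, but the record was not available here. A reader might infer that the trial has no primary outcome; the document supports only that none is stated in it.

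A third concerns the comparison of SCIT with TAFT. A reader might infer that the two arms are never compared except with adjustment for alliance. That goes too far: the three-arm interaction includes their difference. What is absent is a contrast that isolates it. A reader might also infer that the group coefficient in the alliance regression is meant as the treatment comparison. The plan gives that regression a different purpose, and nothing in the document proposes such a use.

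Finally, the paired-test disagreement is not a fixed rate. When TAU improves by 0.2 SD it falls to 3-6%, about the false-positive rate of the direct contrast. This limits the size of the problem. It does not turn a within-arm test into a comparison of arms.

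**Conclusion.** The concern holds in a limited form. The plan tests five equally ranked outcomes without a stated error rate, and its only stated follow-up does not answer the specificity question that it poses.

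Under 0.05 per test and an any-one-counts rule, the chance of at least one false interaction runs from 22.6% for independent outcomes, through about 19-21% at moderate correlation, to about 10% at correlation 0.9. These are conditional figures, not properties of the plan as written. If time effects also count as findings, the rates are higher.

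The missing pairwise contrast does not depend on those assumptions: it follows from the text. How often the within-arm tests would mislead does depend on them, so 13-16% should be quoted only with its conditions (30 per arm, no change in TAU) and beside the 3-6% and 8-29% of the other two cases.

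This should be corrected in the analysis and reporting. Confidence is medium, because the registration could not be checked and the sample size is not given.

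**What to change.** State that the group-by-time interaction, not the time main effect, triggers follow-up. For an outcome that passes, test the contrasts of change SCIT-TAFT, SCIT-TAU and TAFT-TAU with the pooled error of that ANOVA, at the same level as the interaction. Claim an effect only for the outcome and contrast that pass. Report time effects and within-arm paired t tests as descriptive.

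State one rule across outcomes. Two that work are 0.05/5 = 0.01 for each of the five, with one named score per instrument, or 0.05/2 = 0.025 for each of two named outcomes, one for functioning and one for quality of life, with the mediators secondary. With three arms, either keeps the overall rate at or below about 5% for interactions and contrasts together. The choice between them is partly preference. It should be reconciled with any registered primary outcome.

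Label the alliance regression exploratory, including its group coefficient, and do not use that coefficient as the SCIT-TAFT comparison. TAFT targets the alliance, so the adjustment variables may themselves be affected by arm.

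No new data are needed: p-values are read against a stated threshold and three contrasts are added per passing outcome. The cost is lower power per outcome, and under the two-outcome rule the mediator results carry no confirmatory claim. The Research Setting section says "Data were collected between the years 2014 and 2018", so if results have been seen, the rule must be labelled post hoc. It then corrects the error rate but does not make the family prespecified, and its practical effect may be to relabel some nominal findings as exploratory.
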